## **8.8 Trial Duration**

An individual subject's participation will involve 6 visits over approximately a 52-week period. After the trial, subjects will be treated according to standard of care, at the discretion of the treating physician. The total duration of the trial from FSFV until LSLV is expected to be 18 months.

## 9 ADVERSE EVENTS

### 9.1 Adverse Event

An adverse event (AE) is defined as any untoward medical occurrence associated with the use of a drug in humans, whether or not the event is considered drug-related. An AE can therefore be any unfavorable and unintended sign (e.g. an abnormal laboratory finding), symptom, or disease occurring after the subject signature of the ICF without any judgment on causality.

AEs ongoing at the time of Visit 4 (Day 57) in trial NVU-003 and prior to IMP administration at Visit 1 of NVU-004 will not be considered an AE for NVU-004. These will be recorded as medical history in NVU-004. If there is a worsening of such medical history after administration of the IMP, this should be considered a new AE and reported.

Worsening of DED will be considered an AE only if the dry eye status of the subject exceeds their previous experiences with the condition. This will be determined by the subject and the investigator.

A clinically significant visual acuity worsening in NVU-004 (defined as an increase of 0.22 or greater in logMAR score) from Visit 0 in NVU-003 will be considered an Adverse Event.

Documentation regarding the AE should be made as to the nature, date of onset, end date, severity, relationship to IMP, expectedness, action(s) taken, seriousness, and outcome of any sign or symptom observed by the physician or reported by the subject upon non-leading AE questioning.

AEs (both elicited and observed) will be monitored throughout the trial. The investigator will promptly review all AEs for accuracy and completeness. All AEs will be documented on the appropriate source document and eCRF.

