#### 10.4.5 Primary Safety Analyses

All safety analyses will be performed on the Safety Population.

Dosing information will be summarized overall and by treatment from NVU-003 and listed for each subject. Discontinuation of treatment will be summarized. The primary reason for IMP discontinuation will also be summarized by treatment group as received in NVU-003. Adverse events (AEs) will be coded using the MedDRA dictionary. An AE will be defined as treatment emergent if it occurs or worsens after the first dose of trial treatment in clinical trial NVU-004.

Frequencies and percentages of subjects with TEAEs, treatment related TEAEs, serious TEAEs, and TEAEs causing premature discontinuation will be provided. Furthermore, frequencies will be given of subjects with TEAEs by system organ class; by system organ class and preferred term; by system organ class, preferred term and maximal severity; by system organ class, preferred term and strongest relationship; and by system organ class, preferred term, maximal severity, and strongest relationship. Separate summaries will be provided for ocular and non-ocular AEs. Ocular AEs will be summarized at the subject level, at the eye level, and separately for study and fellow eyes.

The treatment groups as assigned in NVU-003 will be compared descriptively with regard to safety endpoints. No inferential comparison will be conducted.

Concomitant medications will be coded using the most recent version of WHO-Drug Dictionary.

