### LogMAR Visual Acuity Calculations

The last line in which a letter is read correctly will be taken as the base logMAR reading. To this value will be added the number "N x 0.02" where 'N' represents the total number of letters missed up to and including in the last line read. This total sum represents the logMAR visual acuity for that eye.

For Example: Subject correctly reads 4 of 5 letters on the 0.2 line, and 2 of 5 letters on the 0.1 line.

Base logMAR	= 0.1
N (total number of letters incorrect on line 0.2 and on line 0.1)	= 4
N x T (T=0.02)	= 0.08
Base logMAR + (N x T)	= 0.1 + 0.08
logMAR VA	= 0.18

Repeat the procedure for the left eye (OS).

In order to provide standardized and well-controlled assessments of visual acuity during the study, all visual acuity assessments at a single site must be consistently done using the same lighting conditions and same correction if possible during the entire study. If the same correction cannot be used (i.e. a subject forgets his/her glasses), the reason for the change in correction should be documented.

Note: A clinically significant visual acuity decrease (defined as an increase of 0.22 or greater in logMAR score) from Visit 0 (NVU-003) will be considered an Adverse Event.

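### The 0.22 logMAR acuity AE rule is measured from NVU-003 Visit 0, but the carry-over and treatment-emergent rules run from the first NVU-004 dose, and the documents do not reconcile them

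*Combined protocol and SAP*

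**What the plan says.** Four statements in the combined protocol and SAP bear on this.

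- **Acuity rule, Section 9.1.** The sentence begins "A clinically significant visual acuity worsening in NVU-004" and continues "defined as an increase of 0.22 or greater in logMAR score) from Visit 0 in NVU-003 will be considered an Adverse Event".
- **Acuity rule, Appendix 3 (LogMAR Visual Acuity Calculations).** The note has the same threshold and the same reference visit, "defined as an increase of 0.22 or greater in logMAR score) from Visit 0 (NVU-003) will be considered an Adverse Event", but does not say that the worsening must occur in NVU-004.
- **Carry-over rule, Section 9.1.** An AE still ongoing at NVU-003 Visit 4, before the first NVU-004 dose, "will not be considered an AE for NVU-004. These will be recorded as medical history in NVU-004". If it worsens after dosing, it becomes a new AE.
- **Treatment emergence, Section 10.4.5.** An AE counts if "it occurs or worsens after the first dose of trial treatment in clinical trial NVU-004".

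AEs are the primary endpoint (Section 6.1). The Day 57 acuity reading from NVU-003 is transferred as the NVU-004 Visit 1 (Day 1) value (Section 4.3, Appendix 1), and acuity is measured again at Visits 2 to 6. Section 10.4.1 sets baseline for all change scores before treatment in NVU-003. For entry, exclusion 11 tests only the absolute acuity level in both eyes; exclusions 2 and 12 leave room for investigator judgment.

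**The concern.** The acuity rule has one starting point, and the two rules that decide whether an event belongs to NVU-004 have another. Eight weeks of masked treatment lie between them. Two problems follow.

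First, a loss that arose during NVU-003 and then stays stable may be recorded in two ways. The Appendix 3 note, taken alone, calls it an AE; the carry-over rule calls it medical history if it was an ongoing AE. No passage says which prevails, and the Visit 1 instructions in Section 8.4.1 send sites to Section 9.1 for this decision.

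Second, a subject whose acuity improved during NVU-003 must lose that gain and a further 0.22 before the rule fires. This matters most for subjects who received saline in NVU-003, because NVU-004 Day 1 is the start of their NOV03 exposure and the interval back to Visit 0 contains no NOV03.

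What is at stake is consistent recording of an ocular safety signal on the primary endpoint. The same safety analyses also feed the 26-week interim report intended for the initial NDA (Section 10.4.10).

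**Working it through.** **Inputs.** Threshold 0.22 logMAR, reference NVU-003 Visit 0 (Section 9.1, Appendix 3). One letter = 0.02 logMAR (Appendix 3). About 200 subjects enrolled (Section 10.3).

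**The plan's own figures.** The Appendix 3 scoring example reproduces: 0.1 + 4 × 0.02 = 0.18. The detection statement in Section 10.3 also reproduces: 1 − 0.97^100 = 0.9524, so at least 95%. Neither is in dispute.

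**Threshold in letters.** 0.22 / 0.02 = 11 letters.

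**Loss needed within NVU-004.** Let d be the change from Visit 0 already present at Day 1 (positive = worse). Read literally, the rule fires when d plus the loss since Day 1 is at least 0.22, so the loss needed since Day 1 is 0.22 − d.

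| d at Day 1 | Loss since Day 1 needed to fire |
|---|---|
| −0.14 | 0.36 (18 letters) |
| −0.10 | 0.32 (16 letters) |
| 0 | 0.22 (11 letters) |
| +0.20 | 0.02 (1 letter) |
| +0.22 or more | none |

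**Example A, stable earlier loss.** Visit 0 = 0.10, Day 1 = 0.34, every later visit = 0.34. Change from Visit 0: 0.34 − 0.10 = +0.24. Change since Day 1: 0.34 − 0.34 = 0.

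**Example B, loss wholly on open-label drug.** Visit 0 = 0.20, Day 1 = 0.06, later = 0.40. Change from Visit 0: 0.40 − 0.20 = +0.20, below 0.22. Loss since Day 1: 0.40 − 0.06 = 0.34, or 17 letters.

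**The rules side by side** (changes are from Visit 0):

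| Day 1 → later | Appendix 3 read literally | Section 9.1, worsening in NVU-004 read as new worsening | Carry-over rule |
|---|---|---|---|
| +0.24 → +0.24 (A) | AE | not triggered | medical history, if an ongoing NVU-003 AE |
| +0.24 → +0.26 | AE | AE | new AE, if an ongoing NVU-003 AE |
| +0.20 → +0.22 | AE | AE | silent |
| 0 → +0.22 | AE | AE | silent |
| −0.14 → +0.20 (B) | not triggered | not triggered | silent |

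Only the first row gives opposite answers, and only under the literal reading. The last row is missed under both readings.

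**Effect on the primary tables.** In Example A nothing occurs or worsens after the first NVU-004 dose, so an onset dated to NVU-003 keeps it out of the TEAE tables. It enters only if the site dates onset at an NVU-004 visit. No text tells sites how to date such a loss.

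**Size.** The documents give no rate. If 0.5%, 1%, 3% or 5% of 200 subjects carried a loss like Example A, that would be 1, 2, 6 or 10 subjects. These percentages are assumptions. No count can be given for Example B.

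**The case against.** The strongest reply is that the body text already handles the stable case. Section 9.1 speaks of worsening in NVU-004; a subject who reads 0.34 throughout has not worsened in NVU-004, so the acuity rule and the carry-over rule agree. That is a fair reading. It leaves the Appendix 3 note, which lacks the limiting words and is the text an examiner has in hand when scoring acuity.

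A reader might infer that the same subject is counted in opposite ways on the primary endpoint. The documents do not support that. The conflict arises at AE recording, and the TEAE definition removes the stable case when onset is dated before dosing. The carry-over rule also covers ongoing AEs, not every finding present at Day 57; whether such a loss was an AE in NVU-003 depends on a protocol that is not available here.

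A reader might also infer that a loss like Example B would go unreported. That is too strong. The 0.22 rule states what must be an AE, not what cannot be one. The general definition in Section 9.1 covers any unfavourable sign, and acuity is summarized by visit (Section 10.4.6). What stands is that the one explicit threshold does not catch it, and the change-from-baseline summaries do not recover it because they too refer to NVU-003.

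Nor is entry of subjects with an earlier loss unrestricted: exclusions 2 and 12 allow an investigator to keep them out. But they set no limit on change since Visit 0.

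Finally, Visit 0 is a defensible reference. It matches the baseline in Section 10.4.1 and captures cumulative loss in subjects already on NOV03. That argues for keeping it, not against adding Day 1.

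**Conclusion.** The concern holds in limited form. The acuity rule is anchored to NVU-003 Visit 0, the carry-over and TEAE rules are anchored to the first NVU-004 dose, and no passage reconciles them.

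- A loss of 11 letters or more already present at Day 1 and unchanged afterwards is an NVU-004 AE under the literal Appendix 3 note, and medical history under Section 9.1 if it was an ongoing NVU-003 AE. It affects the primary tables only through the onset date.
- On either reading, some losses of 0.22 or more that arise wholly on open-label NOV03 are not flagged, as with the 17 letters in Example B. Their capture rests on investigator judgment.

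The frequency of both is unknown; the 1 to 10 subjects shown for the first case rest on assumed rates. The documents do not show that the primary tables will be wrong or that sites will in fact classify differently. They show that the instruction permits it, and that the numeric safeguard is weakest where acuity improved in NVU-003. This should be fixed, given how little it costs.

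**What to change.** 1. Bring the Appendix 3 note into line with Section 9.1, and both into line with the TEAE definition in Section 10.4.5.
2. State that a loss of 0.22 or more from NVU-003 Visit 0 already present at NVU-004 Visit 1 is recorded as medical history, with onset dated before the first NVU-004 dose, and is a new AE only if it worsens afterwards.
3. Keep the Visit 0 reference for cumulative loss, and also apply the existing 0.22 threshold to change from NVU-004 Visit 1. Example A is then medical history, and Example B is flagged (0.34 is at least 0.22).

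**Cost.** Wording in two places and one eCRF edit check. The Visit 1 reading is already transferred, so nothing new is measured. The added trigger will flag more acuity events, some from measurement variability. As an illustration, assume no true change, normal differences between two readings, independent eyes and a cut at 0.21 for the 0.02 grid. The chance that either eye is flagged at one visit is 1 − Φ(0.21/SD)², where Φ is the standard normal distribution function. For assumed SDs of 0.05, 0.08, 0.10 and 0.12 this gives about 0, 1.7, 7.1 and 15.7 of 200 subjects. The documents give no SD, and the existing Visit 0 trigger carries the same kind of noise. Marking in the listing which reference triggered each event would let readers judge this.

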#### 9.1.1 Severity

Severity of an AE is defined as a qualitative assessment of the degree of intensity of an AE as determined by the investigator or reported to him/her by the subject. The assessment of severity is made irrespective of relationship to IMP or seriousness of the event and should be evaluated according to the following scale:

- *Mild*: Event is noticeable to the subject but is easily tolerated and does not interfere with the subject's daily activities.
- *Moderate*: Event is bothersome, possibly requiring additional therapy, and may interfere with the subject's daily activities.
- *Severe*: Event is intolerable, necessitates additional therapy or alteration of therapy, and interferes with the subject's daily activities.

### 9.1.2 Relationship to Investigational Product

The relationship of each AE to the investigational drug should be determined by the investigator using these explanations:

- *Suspected*: A reasonable possibility exists that the investigational product caused the AE.
- *Not Suspected*: A reasonable possibility does not exist that the investigational product caused the AE.

Suspected adverse reaction means any AE for which there is a reasonable possibility that the investigational product caused the AE. “Reasonable possibility” means there is evidence to suggest a causal relationship between the investigational product and the AE. Types of evidence that would suggest a causal relationship between the investigational product and the AE include: a single occurrence of an event that is uncommon and known to be strongly associated with IMP exposure (e.g. angioedema, hepatic injury, Stevens-Johnson Syndrome); one or more occurrences of an event that is not commonly associated with IMP exposure, but is otherwise uncommon in the population exposed to the IMP (e.g. tendon rupture); an aggregate analysis of specific events observed in a clinical trial (such as known consequences of the underlying disease or condition under investigation or other events that commonly occur in the trial population independent of drug therapy) that indicates those events occur more frequently in the IMP-treatment group than in a concurrent or historical control group.

### 9.1.3 Expectedness

The expectedness of an AE should be determined based upon existing safety information about the IMP. The active ingredient of NOV03 is perfluorohexyloctane, which is a semifluorinated alkane with a well-established tolerability and safety profile. It has been tested in four PMCF studies and one phase 2 clinical trial up to now with >370 subjects that received NOV03 treatment. AEs of those studies have been listed in the Investigator’s Brochure. Therefore, the following definitions will be used:

- *Unexpected*: An AE that is not listed in the investigator’s brochure in the Adverse Reaction Section at the specificity or severity that has been observed.
- *Expected*: An AE that is listed in the investigator’s brochure in the Adverse Reaction Section at the specificity and severity that has been observed.

The investigator should initially classify the expectedness of an AE, but the final classification is subject to the sponsor’s determination.

### 9.1.4 Outcome

The outcome of any AE will be determined and recorded using the following categories:

- Recovered/Resolved
- Recovering/Resolving
- Not Recovered/Not Resolved

- Recovered/Resolved with Sequelae
- Lost to Follow-up
- Fatal
- Unknown

## 9.2 Serious Adverse Events

An AE is considered serious if, in the view of either the investigator, medical monitor or sponsor, it results in any of the following outcomes:

- Death;
- A life-threatening AE;
  - Note: An AE is considered “life-threatening” if, in the view of either the investigator, medical monitor or sponsor, its occurrence places the subject at immediate risk of death. It does not include an AE that, had it occurred in a more severe form, might have caused death.
- Inpatient hospitalization or prolongation of existing hospitalization;
  - Note: The term “inpatient hospitalization” refers to any inpatient admission (even if less than 24 hours). For chronic or long-term inpatients, inpatient admission includes transfer within the hospital to an acute/intensive care inpatient unit. Inpatient hospitalization does not include: emergency room visits; outpatient/same-day/ambulatory procedures; observation/short stay units; rehabilitation facilities; hospice facilities; nursing homes; or clinical research/phase 1 units.
  - Note: The term “prolongation of existing hospitalization” refers to any extension of an inpatient hospitalization beyond the stay anticipated or required for the reason for the initial admission as determined by the investigator or treating physician;
- A persistent or significant incapacity or substantial disruption of the ability to conduct normal life functions;
  - Note: A serious adverse event (SAE) specifically related to visual threat would be interpreted as any potential impairment or damage to the subject’s eyes (e.g. hemorrhage, retinal detachment, central corneal ulcer or damage to the optic nerve).
- A congenital anomaly/birth defect;
- Medically important
  - Important Medical Events that may not result in death, be life-threatening, or require hospitalization may be considered serious when, based upon appropriate medical judgment, they may jeopardize the subject and may require medical or surgical intervention to prevent one of the outcomes listed in this definition. Examples of such medical events include allergic bronchospasm requiring intensive treatment in an emergency room or at home, blood dyscrasias or convulsions that do not result in inpatient hospitalization, or the development of drug dependency or drug abuse.

### 9.3 Procedures for Reporting Adverse Events and Serious Adverse Events

All AEs and their outcomes must be reported to CRO, the trial sponsor, and the IRB/IEC as required by the IRB/IEC, federal, state, or local regulations and governing health authorities and recorded on the appropriate source document and eCRF page.

#### 9.3.1 Reporting a Serious Adverse Event

To ensure subject safety, all SAEs, regardless of relationship to the IMP, must be immediately (i.e. within a maximum 24 HOURS after becoming aware of the event) reported to CRO Drug Safety Navigator (who will notify the medical monitor and the trial sponsor). All information relevant to the SAE must be recorded on the appropriate SAE report form. The CRO Drug Safety Navigator will forward the documentation to the medical monitor and the sponsor for review. Within 24 hours of knowledge of a new SAE, the investigator must enter the SAE information onto the hard copy SAE report form and transmit the form to the SAE Fax number below. The investigator must verify the report was received by CRO Drug Safety Navigator. If the investigator is not able to successfully fax the SAE Report or verify it was successfully received by CRO Drug Safety Navigator, the investigator must call the CRO SAE Hot Line to report the SAE and follow-up with the CRO Drug Safety Navigator Associate by phone (**see phone/fax numbers and email in safety management plan (SMP)**).

The information entered must contain sufficient information to enable medical assessment by the medical monitor. At a minimum, the initial SAE report should contain the following information:

- Subject's trial ID number
- Description of the Serious Adverse Event
- Date of the Serious Adverse Event
- Criterion for seriousness
- Preliminary assignment of causality to IMP

All information relevant to the SAE must be recorded on the appropriate case report forms. The investigator is obligated to pursue and obtain information requested by CRO Drug Safety Navigator, CRO and/or the sponsor in addition to that information reported on the case report form. All subjects experiencing a SAE must be followed up and the outcome reported.

The investigator must obtain and maintain in his/her files all pertinent medical records, information, and medical judgments from colleagues who assisted in the treatment and follow-up of the subject; provide CRO Drug Safety Navigator and the trial sponsor with a complete case history, which includes a statement as to whether the event was or was not suspected to be related to the use of the IMP; and inform the IRB of the AE within their guidelines for reporting SAEs.

All SAEs will be reported as of the signature of Informed Consent. All SAEs will be followed until resolution, stabilization, the event is otherwise, explained, or the subject is lost to follow-up.

### 9.3.2 Reporting a Suspected Unexpected Serious Adverse Reaction (SUSAR)

All SAEs that are ‘suspected’ (relationship to drug of definite, probable or possible) and ‘unexpected’ are to be reported to CRO Drug Safety Navigator within 24 hours after the site becomes aware of the event, via the SAE reporting process outlined above. All SAE/SUSARs will be promptly reported to the IRB/IEC and governing health authorities (e.g. United States Food and Drug Administration [FDA]) as required by the IRB/IEC, federal, state, and local regulations and timelines.

## **9.4 Procedures for Unmasking of IMP**

All subjects, investigators, and trial personnel involved with the conduct of the trial will be unmasked as this is a single-arm and open label extension trial.

## **9.5 Type and Duration of the Follow-up of Subjects after Adverse Events**

The investigator will follow unresolved AEs to resolution until the subject is lost to follow-up or until the AE is otherwise classified. Resolution means the subject has returned to baseline state of health or the investigator does not expect any further improvement or worsening of the AE. If the subject is lost to follow-up, the investigator should make 3 reasonable attempts to contact the subject via telephone, post, or certified mail. All follow-up will be documented in the subject’s source document. Non-serious AEs identified on the last scheduled contact must be recorded on the AE eCRF with the status noted.

If the investigator becomes aware of any new information regarding an existing SAE (i.e. resolution, change in condition, or new treatment), a new SAE Report Form must be completed and faxed to CRO Drug Safety Navigator within 24 hours of the site’s awareness of the new information. The original SAE form is not to be altered, but a new SAE Report Form must be completed and identified consecutively based on the previous report form (i.e. Initial Report, Follow-up #1, Follow-up #2, etc.). The report must describe whether the event has resolved or continues and how the event was treated.

